5.1.5. Analyses of Secondary Outcomes

We will use the same approach described in the primary outcome analysis to compare the number of days of opioid treatment with only infants receiving morphine as the primary pharmacological treatment for NOWS (Secondary Outcome 1). We will use this same approach to compare the number of days of opioid treatment using only infants receiving methadone as the primary pharmacological treatment for NOWS (Secondary Outcome 2).

We will use adjusted logistic regression models to provide an odds ratio (OR) and 95% Confidence Intervals (CI) for binary secondary outcomes measured only once. These outcomes will include:

- the proportion of infants by intervention arms that escalate or resume opioid medication during weaning,
- for the proportion of infants by intervention arms with an atypical neurobehavioral profile (**Profile 5, Figure 1**),
- the proportion of infants who receive an escalation of a second-line or third-line drug to treat NOWS signs from the first weaning dose to cessation of opioid.

Title: Pragmatic, Randomized, Blinded Trial to Shorten Pharmacologic Treatment of Newborns with Neonatal Opioid Withdrawal Syndrome (NOWS)

Sponsor: National Institutes of Health

We will adjust these models for the stratification variable (hospital), covariates of maternal treatment and stabilization dose, and baseline variables that may differ between groups by chance. We define the covariates that we may adjust for earlier in this section in the paragraph on other collected data.

We will analyze the secondary outcome of the total opioid exposure from the first weaning dose to cessation of opioid in a similar manner as the primary outcome. We will use a regression model that will include: a fixed treatment effect (intervention arms) and adjustment for the stratifying variable, covariates of maternal treatment and stabilization dose, and baseline variables that may differ between groups by chance as fixed effects. We will include hospital (site) as a random effect. The primary test of interest will be the F-test of the intervention arm effect, and we will report the treatment difference along with 95% CI.

We will measure the secondary outcome of maternal well-being and maternal- infant attachment by using PROMIS Measures and MPAQ total scores. We will analyze these in a similar manner as the primary outcome. We will use a regression model to analyze PROMIS Measures and MPAQ total scores. This model will include a fixed treatment effect (intervention arms), an adjustment for the stratifying variable, and fixed effects for the covariates of maternal treatment and stabilization dose. The PROMIS Measures outcomes are measured at 1-month after discharge and 24-months of age. The models for PROMIS Measures outcomes will include the 1-month after discharge PROMIS Measures outcome as a covariate. The F-test of the intervention arm effect will be the primary test of interest. We will report the intervention arm difference along with 95% CI. We will conduct analyses among the entire group and among those where the biologic mother is the primary caretaker.

We will measure the secondary outcome of infant neurobehavioral functioning using BITSEA scores. The BITSEA consists of two multi-item scales, a Problem scale (31 items) and a Competence scale (11 items). A high score on the Problem scale or a low score on the Competence scale is less favorable. We will analyze these in a similar manner as the primary outcome. We will use regression models to analyze the BITSEA total and subscale scores. This model will include a fixed treatment effect (intervention arms), an adjustment for the stratifying variable, and fixed effects for the covariates of maternal treatment and stabilization dose. The F-test of the intervention arm effect will be the primary test of interest. We will report the intervention arm difference along with 95% CI. We will conduct analyses among the entire group and among those where the biologic mother is the primary caretaker.

We will calculate binomial proportion and their corresponding 95% CI by intervention arm for each of the following safety adverse events: seizures (clinical or EEG), excessive stool output, respiratory disturbances, and feeding tolerance. We will use chi-square tests to compare the proportion of seizures (clinical or EEG), excessive stool output, respiratory disturbances, and feeding tolerances between intervention arms. In addition to unadjusted analyses, we will compare AEs across the weaning interventions by using adjusted logistic regression models that adjust for the stratification variable (hospital), covariates of maternal treatment and stabilization dose, and possibly any baseline variables that were significantly different between weaning interventions. We define covariates that we may adjust for earlier in this section within the paragraph on other collected data.

We will analyze the length of hospital stay in a similar manner as the primary outcome. We will use a simple, unadjusted regression model to analyze the total length of stay and will include a fixed treatment effect (intervention arms). A second regression model will include a fixed treatment effect and will include adjustment for the stratifying variable and covariates of maternal treatment and

stabilization dose. The F-test of the treatment effect will be the primary test of interest. We will report the treatment difference along with 95% CI. Sensitivity analysis will involve time-to-event analyses using survival models to account for skewness and possible censoring of each outcome.

We will analyze the caregiver questionnaire outcomes and the death outcome using a longitudinal GLMM or GEE model appropriate for the outcome type since the data will be collected at multiple time points after discharge. Count data that tend to have more than 0 or 1 events counted will be analyzed using a Poisson model while binary or count data that rarely goes beyond 1 occurrence will be analyzed using a Logistic model. In case of count data that rarely goes beyond 1 occurrence, this data will be transformed to binary data (occurrence/no occurrence). We will present mean outcome ratios for count data (from Poisson models) and odds ratios for binary data (from logistic models) with respect to the intervention effect as well as 95% CI of the intervention effect. All analyses will be adjusted for repeated measures over time, so that patterns of change for these outcomes over time can be assessed by treatment group.

In addition to time of discharge and 24 months of age, anthropometric outcomes will be measured at birth. We will calculate anthropometric z-scores at each of the three assessment periods for the purpose of analysis based on age and gender specific WHO norms. The approach to analyzing weight is given next.

We will provide the mean and SD of infants' weights (z-scores) separately for each treatment group. We will use a mixed linear model to evaluate the effect of treatment arm on weight (z-scores). The model will examine how the treatment means differ (i.e., main treatment effect), how treatment means change over time (i.e., main time effect), and how differences between treatment means change over time (i.e., treatment-by-time effect). We will carry out assessment across 3 time points: birth, hospital discharge, and 24 months of age. The mixed model longitudinal analytical approach allows us to analyze correlated data obtained repeatedly from the same participant and account for the ICC among participants nested within with same clinical site. To account for potential imbalance in key demographic and site-level characteristics, unadjusted and adjusted GLMMs will be fit to the data. Initially, the unadjusted mixed model will include the fixed categorical effects of intervention, time, and intervention-by-time interaction and the random-site effect. We will calculate the point estimates and their respective CIs for the changes in infants' weights for each intervention group and for the difference in the estimated change between intervention groups. Additionally, the team will present the p-value of the difference in point estimates between intervention groups.

We will examine the impact of the treatment arm on length, HC, and infant weight for length (z-scores) using the same analytical methods described for weight (z-scores) above. Additionally, we will provide the mean and SD of infant BMI-z at 24-months for each treatment group. The team will use a GLMM with an identity link to compare average BMI-z between the groups, and the team will report point estimates for the group mean difference along with a 95% CI.

To compare Bayley-IV scores between intervention arms, we will perform a linear mixed-effects model with a fixed effect for the intervention group and a random effect for study site. We will report point estimates for the group mean difference along with a 95% CI, and the team will repeat this analytical approach for each of the Bayley-IV domains.

Descriptive statistics (means, medians, SD, percentiles) for continuous secondary outcomes and frequency based statistics (N and percentages) for binary secondary outcomes will be generated and summarized in a tabular form by treatment group.

5.1.6. Bayesian Analyses

Other randomized trials of NOWS have ended prior to meeting the projected enrollment, indicating the challenges in studying this population (15, 17, and 18). In case of insufficient enrollment, we will pre-specify Bayesian analyses of the final data in addition to the frequentist analyses, defined above. Below, we first define the Bayesian analyses that will mirror the above defined frequentist analyses of the primary outcome.

We will analyze the primary outcome with a linear regression that will include treatment group (intervention arms), stabilization dose and maternal treatment as covariates, and we will include hospital as a random effect. We will use a neutral prior for treatment effect that is centered at a mean difference of 0 and a standard deviation of three, normal ($\mu=0$, $\sigma=3$) distribution. For the intercept term, we will use a normal ($\mu=0$, $\sigma=10$) prior. For all other baseline covariates in the model, we will use weakly informative neutral normal ($\mu=0$, $\sigma=2$) priors. We will use a weakly informative half-normal ($\mu=0$, $\sigma=1$) prior for the standard deviation of the random hospital effect. For all models, we will report posterior medians and 95% credible intervals (CrI) for the group mean differences and the probability that a rapid-wean intervention will reduce the days of opioid treatment, compared to a slow-wean intervention. For sensitivity analyses, we will analyze the primary outcome with skeptical and enthusiastic priors. We will center the skeptical prior at a mean difference of two, indicating the view of a skeptic with belief that the study intervention will increase the number of days of opioid treatment by two days. We will center the enthusiastic prior at a mean difference of -2, meaning a priori that an enthusiast expects the study intervention to reduce the number of days of opioid treatment by two days. In both the enthusiastic and skeptic priors, the standard deviation will be three. As with the primary frequentist analysis, sensitivity analyses may be done using Bayesian analyses, where normal ($\mu=0$, $\sigma=2$) priors will be placed on all covariates.

Subgroup analysis for secondary outcomes 1 and 2: To estimate possible treatment effect heterogeneity for the primary outcome, we will use a Bayesian hierarchical model with main effects and interaction term between intervention group and type of narcotic (morphine or methadone). This approach allows us to specify a priori how likely (or unlikely) it is for subgroup differences to be present and to shrink the subgroup estimates to the overall mean treatment effect. We will specify a model that allows different standard deviations of the outcome for the two subgroups (as observed in Davis et al). Prior distributions for main effects will be the same as for the primary outcome. Neutral and skeptical priors will be used for the interaction terms. Point estimates of treatment effect and 95% credible intervals will be reported for each subgroup along with probability of subgroup treatment differences.

We will analyze secondary binary outcomes with Bayesian logistic regression models, including treatment group, maternal treatment, and stratification dose as covariates, and we will include hospital as a random effect. We will use a neutral prior centered at 1.0 with 95% CrI of 0.33-3.0 (to allow for large range of ORs) for the treatment effect. In the log OR scale, this prior will be normal (0, SD=0.57), and all other priors will be the same as above.

We will analyze secondary outcomes of the total opioid exposure and assessments of maternal well-being, maternal-infant attachment, infant neurobehavioral functioning, infant development, and growth with a similar linear regression model used for the primary outcome.

We will analyze secondary outcome of length of stay with a linear regression model similar to the one used to analyze the primary outcome; however, we will also fit survival analysis models to study the effects of skewness.

We will implement all Bayesian models via Markov chain Monte Carlo methods (MCMC) by using R or SAS software. For SAS, the procedure will be PROC MCMC. For R, possible software is 'RJAGS' which is an interface to JAGS MCMC software, 'rstan,' 'rstanarm' and 'brms,' which are packages that interface with the Stan language. For each analysis, we will run three MCMC chains with randomly drawn starting values. We will use a burn-in of 3,000 iterations, with sampling from a further 30,000 iterations for each chain. Thinning will be used as necessary to reduce autocorrelation among the samples to improve posterior sampling. To monitor convergence, we will use trace plots and the Gelman-Rubin convergence diagnostic ($R_{hat} < 1.1$ indicating convergence) for all parameters.

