- We will provide each hospital’s pharmacy a dosing calculator (**Appendix 8**). After randomization, the pharmacy will input the weaning intervention (wean by 10% or 15% of the stabilization dose), the stabilization dose (mg/kg/day), the infant’s weight, and the dosing interval (every 3, 4, 8, or 12 hours) to identify the steps of the intervention arm. The dosing calculator will provide the absolute dose (mg) at each step of the intervention arm.
- Frequency of dose changes for **weaning**:
 - We will encourage clinical teams to wean study drug at least every 24 hours.
 - Clinical teams may wean infants at ≤ 24 hours of a given dose (< 8 doses when given every 3 hours, < 6 doses when given every 4 hours, < 3 doses when given every 8 hours and < 2 doses when given every 12 hours), per hospital guideline.
 - Infants not weaned by 24 hours of a given dose will enter a 12-hour period of study protocol guidelines (**Figure 4**). During this 12-hour period, the clinical team **must** wean infants who do not meet hospital specific criteria for escalation. Hospitals do not need to use the total 12-hour period to either wean or escalate if the infant meets the criteria prior to 12 hours. The research team will use dedicated in-services for all clinical teams of participating hospitals prior to study start on the specifics of the trial intervention including the 12-hour study protocol guideline.
 - The clinical team will order, “wean opioid per protocol” to trigger weaning.

[figure not shown]

Figure 4. Overview of the Time Periods Used by Clinical Team to Either Wean or Escalate Study Drug. A 24-hour period for weaning or escalation, per hospital guidelines (light blue bar). Multiple vertical green lines represent dosing intervals; in this example the infant is receiving an opioid every 3 hours. If the opioid dose does not change after 24 hours of dosing, the infant enters a 12-hour period of study protocol guideline (purple bar) to ensure that hospitals either wean or escalate and do not remain on the same dose. This approach will be applied to both weaning interventions.

- Frequency of dose changes for **escalation**:
 - Clinical teams may escalate the opioid at any time during the study intervention based on hospital guidelines; clinical teams do not need to wait for 24 hours of dosing.
 - The clinical team will order, “Escalate opioid per protocol” to initiate escalation.

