APPENDIX 8. PHARMACY DOSING CALCULATOR

We will provide hospital pharmacies with access to a web based dosing calculator. (see below). Once the research team consents and randomizes an infant, the pharmacist can enter the infant’s dosing weight, drug (medication), dose interval, and stabilization dose (mg/kg/dose) in the appropriate boxes. The pharmacist will only have the option to select morphine or methadone from the program for the drug (medication). Once the drug is selected the pharmacy team will only have the option of selecting the dosing interval matched to each drug. For infants receiving morphine the dosing interval will be either every 3 hours or 4 hours. For infants receiving methadone the dosing interval will be either every 8 hours or 12 hours. Once the pharmacist chooses these variables, the spreadsheet will generate the randomization dose (mg/dose) and the sequential dose reductions for each dose level of the rapid-wean (Image A) and slow-wean (image B) interventions. The calculator also provides the final (cessation) dose of study drug.

The screenshot shows a web-based dosing calculator interface. At the top, there are navigation tabs: ACTNOW-Weaning, RTI_DEV, W002-00766, and Dosing Schedule. Below the tabs, the subject is identified as W002-00766 and the page as Dosing Schedule. The main section is titled 'Calculation Parameters' and lists several input fields with their values and status icons (green checkmarks and red X's):

- Dosing Weight: 2.000 kg
- Drug: Morphine
- Dosing Interval: 3 hrs
- Stabilization Dose: 0.07 mg/dose
- 0.28 mg/kg/day
- Treatment Arm: Rapid Wean
- Final Dose: 0.018 mg/dose

Below the parameters is a table titled 'Weaning Schedule' with the following data:

#	Dosing Level	Dose	Status
1	Stabilization	0.07	✓
2	A	0.06	✓
3	B	0.05	✓
4	C	0.04	✓
5	D	0.03	✓
6	E	0.02	✓
7	Placebo	0.00	✓
8	Placebo	0.00	✓
9	Placebo	0.00	✓

Image A: Rapid Wean

Subject: **W002-00808**
Page: **Dosing Schedule**

Calculation Parameters	
Dosing Weight	2.300 kg
Drug	Methadone
Dosing Interval	12 hrs
Stabilization Dose	0.09 mg/dose
	0.08 mg/kg/day
Treatment Arm	Slow Wean
Final Dose	0.018 mg/dose

[figure not shown]
#	Weaning Schedule Dosing Level	Dose	
1	Stabilization	0.09	✓
2	A	0.08	✓
3	B	0.07	✓
4	C	0.06	✓
5	D	0.06	✓
6	E	0.05	✓
7	F	0.04	✓
8	G	0.03	✓
9	H	0.02	✓

Image B: Slow Wean

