6.4.3 Covariates

All secondary regression models will include the stratification variable (site) as a random effect and will be adjusted for:

- Breastfeeding status
- Stabilization dose, continuous
- Maternal treatment which will be categorized as follow:
 - Methadone use
 - o Buprenorphine ± naloxone
 - Prescribed opioids other than methadone and buprenorphine ± naloxone
 - o None/Unknown

In case of mixing among the 4 groups the following rules will be followed:

- o If methadone is used with other opioid, classify as methadone
- If buprenorphine is used with other opioid, classify as Buprenorphine ± naloxone
- o If methadone is used with buprenorphine, classify based on which drug has been used most proximal to delivery.

Additionally, if the sample size allows, secondary analyses can be adjusted for critical covariates that are substantially imbalanced at baseline (both clinically and statistically significantly different)

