6.4.5 Sensitivity Analysis

Because of censoring and/or partial data collected on withdrawn infants we will perform the following additional analyses:

- 1. Replicate the primary analysis (H1) to include maternal treatment, stabilization dose, and maternal feeding.
- 2. Given the learning curves needed to be successful at this trial, we will run a sensitivity analysis limited to centers that enrolled greater than 10 infants.
- 3. Replicate the primary outcome analysis to evaluate the effect of being part of Eat Sleep Console
- 4. Perform survival analysis using cutoff at 35 days as censoring indicator.
- 5. If sample size allows, competing risk analysis will be performed using Cox proportional hazard model adjusting for the following: parental withdrawal, physician withdrawal, and treatment failure defined as unable to wean by 35 days of methadone/morphine treatment. This analysis will allow for additional inquiry into the intervention effect on the primary outcome while accounting for competing safety and withdrawal risks.
- 6. For H13, perform a sensitivity analysis for all hypotheses by removing follow ups outside the 22-26 weeks window.

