6.5 Bayesian Statistical Methods

6.5.1 Statistical Methods

Due to sample size limitation, the primary outcome (H1) and sensitivity analyses (1) and (2) will be analyzed using Bayesian methods in addition to the frequentist analyses to estimate the posterior distribution for all model parameters. Bayesian models will be fit using Markov chain Monte Carlo methods (MCMC) by using software such as PROC MCMC (SAS) or stan (RSTAN/RSTANARM package in R). Model parameter estimates will be generated by fitting three MCMC chains with randomly drawn starting chain. Each chain will involve 1,000 burn-in iterations and 1,000 additional iterations for each chain. Thinning will be used as necessary to reduce autocorrelation among the samples to produce good sampling of the posterior. Trace plots and Gelman-Rubin convergence diagnostics (Rhat <1.1) for all parameters will be used to monitor convergence. For all models, we will report posterior medians and 95% credible intervals (CrI) for the group difference and the probability that a rapid-wean will reduce the days of opioid treatment, compared to a slow-wean intervention.

Primary outcome (H1)

Linear regression model will be used for the primary outcome with treatment group as fixed effect and as hospital random effect. We will use the following priors:

trt effect ~ Normal (
$$\mu = 0, \sigma = 3$$
)
Intercept ~ Normal ($\mu = 0, \sigma = 10$)

All other covariates ~ Normal ($\mu = 0, \sigma = 2$)

Standard deviation of random effect (hospital) $\sim half - noraml (\mu = 0, \sigma = 1)$

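### The Normal(0, SD 2) covariate prior is called weakly informative, but on stabilization dose with no stated unit or scaling it is informative and weakens the Bayesian dose adjustment by an amount that depends on the unit

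*Protocol*

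**What the plan says.** Protocol 5.1.6 holds the Bayesian analyses ready in case enrolment falls short and intends them to parallel the frequentist analyses of the primary outcome. The linear model contains treatment group, with "stabilization dose and maternal treatment as covariates, and we will include hospital as a random effect". On the covariate coefficients it says: "For all other baseline covariates in the model, we will use weakly informative neutral normal", with mean 0 and SD 2.

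SAP 6.5.1 says that "the primary outcome (H1) and sensitivity analyses (1) and (2) will be analyzed using Bayesian methods", and gives the same prior in the line "All other covariates ~ Normal", again with mean 0 and SD 2. The SAP's Bayesian H1 model has treatment and hospital only. Dose comes in through sensitivity analysis 1 of SAP 6.4.5: "Replicate the primary analysis (H1) to include maternal treatment, stabilization dose, and maternal feeding". Sensitivity analysis 2 restricts the centres and adds no dose term.

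SAP 6.4.3 lists "Stabilization dose, continuous". Neither document centres or scales it, or gives its unit for analysis. Elsewhere the unit varies. Protocol 4.2.6 has the pharmacy enter "the stabilization dose (mg/kg/day", a daily dose. The text of protocol Appendix 8 has the pharmacist enter "stabilization dose (mg/kg/dose) in the appropriate boxes", and the calculator screens in that appendix show mg/dose and mg/kg/day.

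**The concern.** A prior SD of 2 means 2 days per one unit of the covariate. For the indicator covariates (maternal treatment category, breastfeeding) one unit is the full contrast, and 2 days is a reasonable scale. Dose is the one prespecified covariate entered as continuous, and one unit of it (1 mg/kg) is far larger than any dose shown in the documents. The same prior therefore holds the dose coefficient towards zero, and how hard it does so depends on whether dose is recorded per dose or per day.

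The Bayesian analysis was written for under-enrolment, and SAP 3.4 and 3.6 record that this happened. If its adjusted version hardly adjusts for dose, close agreement with the unadjusted result could be reported as robustness to dose when part of it comes from the prior. The frequentist and Bayesian versions would also no longer be parallel.

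The unit matters beyond scale. In Appendices 4-7 the morphine examples are higher per day (0.48 against 0.30 mg/kg/day), while the methadone examples are higher per dose (0.10-0.15 against 0.06-0.08 mg/kg/dose).

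**Working it through.** **Fixing N and SD.** The documents give no figure for the dose coefficient, so I first reproduced the figure that sets N and SD. SAP 3.4 uses SD 6.2, difference 2.0, two-sided 0.05 and 80% power: n per arm = 2 × (1.960 + 0.842)² × 6.2² / 2.0² = 150.9, rounded up to 151, or 302 in total. This matches the SAP.

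**Dose examples in the documents.**
- Appendices 4-7: 0.06, 0.08, 0.10 and 0.15 mg/kg/dose. Multiplied by 8, 6, 3 and 2 doses a day, these are 0.48, 0.48, 0.30 and 0.30 mg/kg/day.
- Appendix 8 screens: 0.07 mg at 2.0 kg and 0.09 mg at 2.3 kg, or about 0.035 and 0.039 mg/kg/dose; the screens show 0.28 and 0.08 mg/kg/day.

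**Assumption.** The documents give no SD of dose among infants. I took the SD of these six examples (0.043 mg/kg/dose; 0.149 mg/kg/day) and varied it from half to one and a half times.

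**What the prior allows.** The 95% range of the dose effect is ±1.96 × 2 × dose contrast.
- mg/kg/dose, full example range: 1.96 × 2 × 0.115 = ±0.45 day; per SD, ±0.17 day.
- mg/kg/day, full example range: 1.96 × 2 × 0.40 = ±1.57 days; per SD, ±0.58 day.

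**How much of the data's slope survives.** Normal approximation with the residual SD set to 6.2 and dose uncorrelated with the other terms: SE = 6.2 / (√302 × dose SD); weight on the data = 2² / (2² + SE²).

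| Unit | Dose SD (assumed) | SE of slope | Weight on data |
|---|---|---|---|
| mg/kg/dose | 0.022 / 0.043 / 0.065 | 16.5 / 8.25 / 5.5 | 1.4% / 5.6% / 11.7% |
| mg/kg/day | 0.075 / 0.149 / 0.224 | 4.78 / 2.39 / 1.59 | 15% / 41% / 61% |
| per 1 SD of dose | 1 | 0.357 | 97% |

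At the central dose SDs, the weights for mg/kg/dose and mg/kg/day are 7% and 48% with the planned 502 infants and SD 6.9, and 4% and 32% with 200 infants and SD 6.2.

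**Effect on the treatment estimate.** I simulated 4,000 trials per setting with N = 302, a true effect of -2 days, total SD 6.2 and no site effect. The assumed dose SDs were 0.044 mg/kg/dose or 0.15 mg/kg/day, and the assumed dose effects 1 or 2 days per SD.
- At 1 day per SD, a true slope of 22.7 per mg/kg/dose is estimated at 1.3 on average, and a true slope of 6.7 per mg/kg/day at 2.8.
- Within each setting, the mean treatment effect is practically the same with unscaled, standardized or no dose term (-1.86 to -1.88). The gap from -2 is mainly the treatment prior.
- In a single trial the unscaled and standardized versions differ on average by 0.05 day (mg/kg/day) or 0.08 day (mg/kg/dose) at 1 day per SD, and by 0.10 or 0.16 day at 2 days per SD. The 95th percentiles run from 0.13 to 0.41 day. The treatment SE is about 0.66.
- At 2 days per SD the SD of the treatment estimate is 0.667 unscaled against 0.638 standardized (mg/kg/dose), and 0.648 against 0.635 (mg/kg/day). At 1 day per SD the loss is about 1% or less.

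**The case against.** The strongest reply is that the documents never say the dose enters unscaled, and do not say in which unit. That is true. Unscaled is the natural reading because no scaling is mentioned, but it is a reading. A reader might infer that the Bayesian analysis does not adjust for dose at all. That comes close only in mg/kg/dose. In mg/kg/day, or in mg/dose as the calculator also shows (about 43% retained at the SD of the six examples), adjustment is weakened but not removed.

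The example doses are also a rough guide. They mix two drugs and four dosing intervals, and protocol 4.2.6 warns that actual doses will probably differ. This is why the dose SD is shown as a range. Every value in that range, in either mg/kg unit, leaves at most 61% of the slope, so the weakly informative label still fails.

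A reader might also infer that the SAP's main Bayesian result is affected, or that the treatment effect is biased. Neither is supported. The SAP's Bayesian H1 model has no dose term. Randomization within hospital keeps the treatment estimate free of average bias from a shrunken dose slope. SAP 6.5.1 runs the Bayesian fits alongside the frequentist ones, so a version of sensitivity analysis 1 without a prior will also exist. These limits stand, and they make the practical effect small.

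**Conclusion.** The point holds as a mismatch between the prior and its description. As written, Normal(0, SD 2) on stabilization dose is informative: about 1-12% of the data's slope survives in mg/kg/dose and about 15-61% in mg/kg/day, so dose adjustment is nearly absent or clearly weakened according to a unit that nobody has fixed. It applies to the protocol's Bayesian primary model and to the SAP's Bayesian sensitivity analysis 1.

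The consequence is modest. Chance dose imbalance is left partly uncorrected, by about 0.05-0.16 day on average against a target effect of 2.0 days, and a little precision is lost, in an analysis that would be reported as dose-adjusted. It is unlikely to change the trial's conclusion.

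These sizes rest on an assumed dose SD, an assumed dose effect of 1-2 days per SD, and N = 302. The documents give neither of the first two, nor the final number enrolled. A smaller N would strengthen the shrinkage.

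**What to change.** In protocol 5.1.6 and SAP 6.5.1:
- State the unit in which stabilization dose is analysed. Protocol 4.2.6 and Appendix 8 give different units and must be reconciled.
- Centre the dose and divide it by its SD over all analysed infants before applying Normal(0, SD 2). For the slope, it is equivalent to leave the dose unscaled and set the prior SD to 2 divided by the dose SD.

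Scaling within drug with a drug indicator is an optional extra. It adds a model term and is not equivalent to rescaling the prior, so it should be decided separately.

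The cost is a sentence in each document and one line of data preparation. No data collection, sample size or error rate changes. If the Bayesian models have already been run, report the unit and scaling used, and rerun those containing dose if it was not scaled.
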